Healthcare providers will be able to provide consent, given the nature and sophistication of their employment and level of education. However, it is important to ensure that hospital patients possess the capacity to provide informed consent. Capacity to consent will be assessed in a systematic format. Immediately excluded from consideration will be new admissions of patients with obvious diagnoses indicating cognitive impairment, ie dementia. To ensure that the respondent has the capacity to provide consent, the study personnel will assess orientation to person, place and date. They will also be administered 3 questions for the Confusion Assessment Method. A positive score on any of these items will trigger an evaluation by an attending psychiatrist who is part of the study team. The evaluation will determine the patient's capacity to provide informed consent. Cases will be treated on a case-by-case basis, and at no point will research assistants make a final decision on cases of questionable capacity to consent. Patients that are determined by a study investigator to not possess the capacity to provide consent will be provided with information on community resources for support and treatment.

A waiver of signed consent will be needed for a subset of patient subjects. This is due to the study being conducted within an acute medical inpatient unit, where conditions that might limit a person's ability to sign the consent form may occasionally occur. This subset of patients will include: patients that are physically unable to write (i.e. hand tremors, spinal cord injury, broken hand, broken shoulder, muscular dystrophy and other physical ailments preventing a patient from physically signing), unable to see (i.e. legally blind, uncontrolled type 2 diabetes mellitus which led to blurred vision), unable to read (i.e. patient does not have their glasses on them).

11. Documentation of Consent/Assent: Specify the documents that will be used during the consent/assent process. Copies of all documents should be appended to the protocol, in the same format that they will be given to subjects.

Compound authorizations attached.

12. Non-English Speaking Subjects: Explain provisions in place to ensure comprehension for research involving non-English speaking subjects. Translated copies of all consent materials must be submitted for approval prior to use. N/A. Only English-speaking subjects will be enrolled in this trial.

13. Consent Waiver: In certain circumstances, the HIC may grant a waiver of signed consent, or a full waiver of consent, depending on the study. If you will request either a waiver of consent, or a waiver of signed consent for this study, complete the appropriate section below.

Not Requesting a consent waiver

- Requesting a waiver of signed consent
- Requesting a full waiver of consent

A. Waiver of signed consent: (Verbal consent from subjects will be obtained. **If PHI is collected, information in this section must match Section VII, Question 6)**

Requesting a waiver of signed consent for Recruitment/Screening only

If requesting a waiver of signed consent, please address the following:

a. Would the signed consent form be the only record linking the subject and the research?

Yes No

b. Does a breach of confidentiality constitute the principal risk to subjects?

Yes No

OR

c. Does the research activity pose greater than minimal risk?

Yes ***If you answered yes, stop. A waiver cannot be granted.*** Please note:

Recruitment/screening is generally a minimal risk research activity

No

AND

d. Does the research include any activities that would require signed consent in a non-research context? Yes No

Requesting a waiver of signed consent for the Entire Study (Note that an information sheet may be required.)

If requesting a waiver of signed consent, please address the following:

a. Would the signed consent form be the only record linking the subject and the research?

Yes No

b. Does a breach of confidentiality constitute the principal risk to subjects?

Yes No

OR

c. Does the research pose greater than minimal risk? Yes ***If you answered yes, stop. A waiver cannot be granted.*** No

AND

d. Does the research include any activities that would require signed consent in a non-research context? Yes No

As mentioned in section 10, a waiver of signed consent will be needed for subjects that are physically unable to provide a signature (i.e. hand tremors, spinal cord injury, broken hand, broken shoulder, muscular dystrophy and other physical ailments preventing a patient from physically signing) or are unable to see (i.e. legally blind, uncontrolled type 2 diabetes mellitus which led to blurred vision), unable to read (i.e. patient does not have their glasses on them). We currently have an information sheet that is provided to this subset of patient subjects.

B. Full waiver of consent: (No consent from subjects will be obtained for the activity.)

Requesting a waiver of consent for Recruitment/Screening only

a. Does the research activity pose greater than minimal risk to subjects?

Yes *If you answered yes, stop. A waiver cannot be granted.* Please note:

Recruitment/screening is generally a minimal risk research activity

No

b. Will the waiver adversely affect subjects' rights and welfare? Yes No

c. Why would the research be impracticable to conduct without the waiver?

We estimate that we will have to screen over 5000 medical inpatients for participation. We further estimate that 20% will be ineligible for screening given the basic exclusion parameters outlined above. The cost and work will be substantially reduced by the initial waiver to determine preliminary ineligibility. Further, it reduces the risk of loss of confidentiality for data collected from subjects who have a planned short hospitalization or have a medical condition that would preclude participation (eg dementia). Information on patients who either are not eligible for screening or refuse participation is immediately destroyed.

d. Where appropriate, how will pertinent information be returned to, or shared with subjects at a later date?

Requesting a full waiver of consent for the Entire Study (Note: If PHI is collected, information here must match Section VII, question 6.)

If requesting a full waiver of consent, please address the following:

a. Does the research pose greater than minimal risk to subjects?

Yes *If you answered yes, stop. A waiver cannot be granted.*

No

b. Will the waiver adversely affect subjects' rights and welfare? Yes No

c. Why would the research be impracticable to conduct without the waiver?

d. Where appropriate, how will pertinent information be returned to, or shared with subjects at a later date?

SECTION VIII: PROTECTION OF RESEARCH SUBJECTS

Confidentiality & Security of Data:

a. What protected health information (medical information along with the HIPAA identifiers) about subjects will be collected and used for the research?

Interview dates, dates of birth, subject names & addresses & contact information, hospital Medical Record Numbers, voice recording.

b. How will the research data be collected, recorded and stored?

All data obtained via paper and pencil, or by digital recordings, will be coded by a unique study number and will be stored in locked filing cabinets in locked research offices. For medical inpatients, all data entered via the computer will also be coded by a unique study identification number. In the event that Healthcare provider's ambitiously record a patient MI session with a non-study subject, the recording will be immediately destroyed from the digital recorded without ever being downloaded to our ITS server. However, this person's de-identified audio-recording consent will be maintained for paper files.

- c. How will the digital data be stored? CD DVD Flash Drive Portable Hard Drive Secured Server Laptop Computer Desktop Computer Other
- d. What methods and procedures will be used to safeguard the confidentiality and security of the identifiable study data and the storage media indicated above during and after the subject's participation in the study?

Data stored on the computer will not contain any identifiable Personal Health Information (PHI). Interview dates, schedules, outcomes, and study progress will be stored in a de-identified tracking database stored on a secure server at Information Technology Services' Data Warehouse Center at Yale University. Contact information and other PHI will be kept in a separate database also located on the secure server at the Data Warehouse Center which is backed-up daily. Access to the server is double password-protected and limited to a select number of authorized Yale staff. All staff accessing the server must use a Yale-managed and owned administrative desktop computer located in the Department of Psychiatry. Similarly, authorized study personnel will be able to access the server via Virtual Private Networks (VPN) configured on Yale-managed and owned laptop computers. Yale VPN provides a method for using a public network (e.g. internet) to securely access a private network (e.g. server). Lastly, Yale University passwords must be changed at least once per calendar year to a different password. This includes primary and responsible Yale-issued NetIDs. Access to Yale's network and affiliated servers will be denied to any staff member who fails to change their password annually. Each year's password must be unique and cannot be similar to previous year's passwords or the new password will not be accepted. Yale's password must have 8-14 characters; must contain at least 2 letters; must contain at least 2 non-letters; must NOT contain Illegal characters < > & \ , ' " : (less than, greater than, ampersand, backslash, comma, apostrophe and quotation marks).

Do all portable devices contain encryption software? Yes No

If no, see <http://hipaa.yale.edu/guidance/policy.html>

- e. What will be done with the data when the research is completed? Are there plans to destroy the identifiable data? If yes, describe how, by whom and when identifiers will be destroyed. If no, describe how the data and/or identifiers will be secured.

Upon completion of the study, files will be destroyed in a manner consistent with HIC policy at that date.

- f. Who will have access to the protected health information (such as the research sponsor, the investigator, the research staff, all research monitors, FDA, Yale Cancer Center Data and Safety Monitoring Committee (DSMC), SSC, etc.)? (please distinguish between PHI and de-identified data)

The databases are stored on an "exclusive" data drive that can only be accessed by authorized Yale-issued NetIDs who work on this study, including the PI, Project Director, and Research Assistants. As an extra safe guard, we will create a "strong" password on the Access study database which is at least 8 characters with at least one uppercase and lowercase letter and one number or symbol. Individual computers that have access to PHI have Pretty Good Privacy (PGP) whole disk encryption installed on them as well as

MXI Security. Therefore, at the time of initial login to the desktop you need to enter your Yale NetID and password and you also need to logon to MXI Security which also requires a password. Failure to logon to MXI Security will prohibit anyone from accessing any of the files on that desktop computer.

g. If appropriate, has a [Certificate of Confidentiality](#) been obtained?

A COC has been obtained and copy has been provided for the HIC.

h. Are any of the study procedures likely to yield information subject to mandatory reporting requirements? (e.g. HIV testing – reporting of communicable diseases; parent interview - incidents of child abuse, elderly abuse, etc.). Please verify to whom such instances will need to be reported. No.

SECTION IX: POTENTIAL BENEFITS

Potential Benefits: Identify any benefits that may be reasonably expected to result from the research, either to the subject(s) or to society at large. (Payment of subjects is not considered a benefit in this context of the risk benefit assessment.)

Integrating substance abuse interventions into primary care could improve health outcomes and reduce health care costs.^{51,52,57,75,76} However, this is contingent upon effective implementation strategies. We will compare and estimate the cost effectiveness of three implementation strategies that have the ability to interdigitate well into a general medical inpatient setting.

This study proposes great value in service delivery and increased medical knowledge to individual patients and their healthcare providers. Substance use increases general medical and psychiatric morbidity. Knowledge about the best methods for implementing evidence-based practices such as motivational interviewing into general medical settings is sorely needed.

Medical inpatients who have a substance use problem may receive a motivational intervention that may enhance their interest in substance use treatment.

Healthcare providers who participate may benefit in the receipt of additional training for motivational interviewing. In addition, they will receive CMEs for didactic training.

SECTION X: RESEARCH ALTERNATIVES AND ECONOMIC CONSIDERATIONS

1. **Alternatives:** What other alternatives are available to the study subjects outside of the research?

Participation in this study is voluntary for Healthcare providers, Hospital Clinical Staff, and hospital inpatients alike and the quality of or general provision of their healthcare is in no way related to their

choice to enroll or not enroll in this RCT. Treatment alternatives include receipt of usual services from hospital social work or CL services.

2. **Payments for Participation (Economic Considerations):** Describe any payments that will be made to subjects, the amount and schedule of payments, and the conditions for receiving this compensation.

Study subjects (patients) will be paid \$30 for their full participation in this study. If a patient prefers not to be paid in cash, they can be reimbursed with a \$30 gift card instead.

Healthcare provider participants will be reimbursed \$350 for baseline assessments, attendance at our high-quality Motivational Interviewing training, and attendance at our baseline focus group. Additionally they will be reimbursed \$50 for completing post-trial assessments and attending a post-trial focus group. Hospital Clinical Staff will be paid \$20 for their participation in focus groups or interviews in this study. These focus groups or interviews may occur up to 3 times throughout the study and therefore they will be paid up to \$60.

3. **Costs for Participation (Economic Considerations):** Clearly describe the subject's costs associated with participation in the research, and the interventions or procedures of the study that will be provided at no cost to subjects.

There are no costs to any study subjects incurred as part of participation in the research.

4. **In Case of Injury:** This section is required for any research involving more than minimal risk.
N/A
 - a. Will medical treatment be available if research-related injury occurs?
 - b. Where and from whom may treatment be obtained?
 - c. Are there any limits to the treatment being provided?
 - d. Who will pay for this treatment?
 - e. How will the medical treatment be accessed by subjects?

This study does not entail physical procedures that may cause injury. No compensation is available for emotional injury. All patients enrolled in study are currently receiving health care at the study-sponsoring hospital.

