- As in previous economic studies conducted by [name],^{95,140-144} including the economic study of our three-arm clinician training trial describe above,⁹⁵ the methodology we will use to estimate the costs of the three MI implementation strategies will be from the perspective of the provider (i.e., hospital) to increase the real-world usefulness of the cost estimates outside of this research protocol.¹⁴⁵ We will not include research costs (e.g., participant reimbursements, assessment measurement) but rather restrict cost estimates to those associated with implementing the three MI implementation strategies. Our cost methodology will follow the micro-costing steps recommended by Yates¹⁴⁶ and Zarkin et al.¹⁴⁷ We will first delineate relevant non-research activities (e.g., MI workshop training, MI interventions, supervision (including expert review of audio recorded Psychiatrists from CL sessions)) and, for each identified activity, we will gather data on both the time spent by personnel in the activities and, as relevant, the space associated with each activity using a modified version of the Resource Allocation Worksheet (RAW) developed for Project COMBINE.¹⁴⁵ This form will collect data on the total labor hours spent on each activity by the trainer, Healthcare providers, and Psychiatrists from CL and the space used in conducting the activity. The labor costs of each activity will be equal to the product of the amount of time spent by each person on the activity and their fully-loaded wage (i.e., including fringe and overhead). To estimate space costs, the research assistant will measure in square feet the size of the rooms used for training, MI interventions, and supervision. We will calculate an average space estimate per medical unit for the main activity domains (workshop training, MI intervention, supervision) and multiply these domains by the annual rent per square foot for the hospital. We will obtain salary data (actual wage plus fringe rate for salary staff and hourly contract rate for contract staff) for Healthcare providers and Psychiatrists from CL and annual rent per square foot from YNHH administrators. We also will record all the direct material expenses (e.g., manuals, rating forms, recording devices, audiotapes) of conducting the MI training workshops and supervisions.

4. **Genetic Testing** N/A

A. Describe

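### The space-cost rule charges each activity domain a full year's rent with no factor for hours used, so Aim 3 incremental costs could be distorted

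*Combined protocol and SAP*

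**What the plan says.** The rule stands in the Combined protocol and SAP, Section V, item 3 (Research Plan), part H, heading 7 (Cost estimates).

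- Measurement: "the research assistant will measure in square feet the size of the rooms used for training, MI interventions, and supervision".
- Aggregation: "We will calculate an average space estimate per medical unit for the main activity domains", the domains being workshop training, MI intervention and supervision.
- Pricing: "multiply these domains by the annual rent per square foot for the hospital".

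Labour, under the same heading, is costed as the "product of the amount of time spent by each person on the activity and their fully-loaded wage". On data collection, the plan says "we will gather data on both the time spent by personnel in the activities and, as relevant, the space associated with each activity"; the instrument is an adapted Resource Allocation Worksheet that records total labour hours and the space used.

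Section V, item 12, part I.3 (Incremental cost-effectiveness analyses) feeds these costs into ICERs against the next-least-costly strategy, into bootstrapped acceptability curves, and into sensitivity analyses on items such as input costs. It adds no rule for allocating space.

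**The concern.** Area in square feet times rent in dollars per square foot per year gives dollars per year. Labour time times wage gives dollars. The two cannot be summed into an activity cost until the space term is multiplied by a length of time. The plan supplies that factor for labour and not for space.

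Cost-effectiveness is the third listed primary aim. H3a and H3b concern which strategy is preferred at low and high threshold values, so they depend on the incremental costs between arms. A space charge matters there if it is large relative to true use and differs between arms. The plan also averages space by medical unit, whereas randomisation is by provider and the PAs work across more than one unit (Section V, item 3, part C). No rule says how a unit-level charge reaches an arm.

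**Working it through.** The plan states no rent, room area, space cost or ICER, so there is no figure to reproduce. The check compares two formulas.

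- As written: area × annual rent.
- Prorated: area × annual rent × U / H, where U is room-hours used and H is room-hours available per year.
- Ratio of the two: H / U. Rent and area drop out.

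**Inputs from the documents.** 10 providers per condition, 40 patients per provider and an estimated 80% receiving MI (item 12, sample size); a 20-minute MI session and a one-day workshop (item 3); in DO ONE, one live supervision per provider and the offer of a second at the halfway point.

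**Assumptions.** H from 2,080 (working hours) to 8,760 (calendar hours); an 8-hour workshop day; 20 minutes per live supervision; one annual charge per domain.

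**Room-hours.** MI sessions in one arm: 10 × 40 × 0.80 = 320; 320 × 20 min = 106.7 h. DO ONE supervision: 10 × 20 min = 3.33 h, or 20 × 20 min = 6.67 h.

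| Domain | U (h) | H/U at 2,080 h | H/U at 8,760 h |
|---|---|---|---|
| MI sessions, one arm | 106.7 | 19.5 | 82.1 |
| One workshop day | 8 | 260 | 1,095 |
| DO ONE supervision, 20 sessions | 6.67 | 312 | 1,314 |
| DO ONE supervision, 10 sessions | 3.33 | 624 | 2,628 |

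**Sensitivity.** At 50% uptake the MI row uses 66.7 h and the ratio is 31.2 to 131.4. At 100% it uses 133.3 h and the ratio is 15.6 to 65.7. If each of 20 supervisions took an assumed hour, U = 20 h and the ratio is 104 to 438.

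**What reaches the increments.**

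- The provider workshop is held constant across conditions, so its space charge largely cancels.
- Supervision does not cancel. DO ONE has live supervision. ORDER ONE depends on CL psychiatrists who receive a two-day workshop, three supervised cases and monthly supervision. SEE ONE has neither component.
- MI-session space should differ between arms, because H1a and H1b expect different uptake. A flat annual charge does not rise with the number of sessions.

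**Illustration only.** Take an assumed supervision room of 100 to 400 sq ft at $20 to $60 per sq ft, so $2,000 to $24,000 a year, charged to DO ONE with SEE ONE as comparator. Using the Table 2 rates, extra criterion sessions are 320 × (0.40 − 0.18) = 70.4. Space then adds $2,000 / 70.4 = $28 to $24,000 / 70.4 = $341 per extra criterion session as written. Prorated at 6.67 h, it adds about $0.02 to $1.09. This shows only that un-prorated space need not be negligible.

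**The case against.** The strongest defence is that this is a short summary in an ethics application. The plan says "Our cost methodology will follow the micro-costing steps recommended by" named sources, draws on the team's earlier economic studies, and collects time alongside space. Those sources may well allocate space by time. That cannot be checked from the documents, and a general citation does not override an explicit multiplication that lacks the term.

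The planned sensitivity analyses do not repair it. Varying the rent rescales every domain by one factor, whereas the ratios at 2,080 hours run from 19.5 to 624. Bootstrapping would carry the same misallocation into every replicate.

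Three stronger readings are tempting and should not be drawn:

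- A reader might infer that every workshop or 20-minute session is billed a year of rent. The text applies the rent to an average area per domain and unit, not to each event.
- A reader might infer that the ICERs are wrong. None is reported, and part of the space cost cancels.
- A reader might infer that the bias falls on DO ONE alone. The costing text counts expert review of recorded CL sessions as supervision, so ORDER ONE carries supervision cost too. DO ONE supervision takes place at the bedside and space is collected only where relevant, so a separate DO ONE room may never be charged.

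**Conclusion.** The rule as written is dimensionally incomplete and, if followed, overstates space cost: about 20 to 82 times for one arm's MI-session domain, and hundreds to thousands of times for a single workshop day or DO ONE live supervision. These factors rest on the assumed 2,080 to 8,760 available hours and, for the last two, on assumed durations. They do not depend on rent or area.

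The consequence for Aim 3 is a possible distortion of incremental costs, ICERs and acceptability curves. Its size and direction cannot be determined, because the documents give no rent, area or cost and no rule for assigning space to arms. The point does not touch the tests in Aims 1 and 2. It is a worthwhile, inexpensive correction to make before costing starts.

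Two related matters are minor clarifications. The labour formula loads wages with overhead while the salary data to be obtained cover wage and fringe, although an overhead rate could be added later. If that overhead includes facilities, space would be counted twice; the plan does not define it.

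**What to change.** Replace the pricing sentence with: space cost = square feet × annual rent per square foot × (room-hours used for the activity / annual available room-hours). Then:

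- State the denominator (working or calendar hours) and use it throughout.
- Add a room-hours field to the Resource Allocation Worksheet. Labour hours are not a substitute: an assumed 8-hour workshop with 10 providers and one trainer is 11 × 8 = 88 person-hours but 8 room-hours, an 11-fold overcharge.
- Assign the prorated cost to the arm that used the space. Include a rule for CL training, which serves ORDER ONE and also prepares the DO ONE supervisors.
- Say whether overhead in the wage excludes facilities, and align the salary data request with the wage definition.

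The cost is one reworded sentence, a few lines of definition and one extra worksheet field. Design, sample size and patient procedures are unaffected.
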